7.6. Study Procedures

7.6.1. Recruitment and Consent

Patients [REDACTED] upon arrival to the center will be approached and consented. The Bridge™ device will be placed immediately on the participant prior to providing comfort medications.

[REDACTED]
The informed consent document will explain that comfort medications may be delayed until the Bridge is placed, as long as the participant is willing to do so. [REDACTED]

The Investigator and/or staff delegated for this task are responsible for conducting the informed consent process and for obtaining written informed consent prior to each participant's inclusion into the study. Subjects must provide written or electronically signed informed consent, as approved by the IRB, prior to being enrolled in the study, in accordance with applicable federal and provincial regulations.

Impact of Bridge™ device as a non-pharmacological approach to treat opioid withdrawal in opioid use disorder (OUD) subjects in an inpatient treatment center

DENE0001

Following identification of a potentially eligible subject as defined by the inclusion and exclusion criteria, the subject will be approached by research staff who will thoroughly explain the purpose, procedures of the study in respect to subject's involvement and responsibilities, potential risks and benefits, and subject's rights and privacy of the data collected. In addition to the full disclosure of the risks and benefits of participating in the study, patients will be informed that their participation is voluntary, and their decision will not impact patient care.

Subjects will be given adequate time to read the informed consent form and ask questions regarding the study. Once all questions have been answered and the informed consent has been signed, the subject will be enrolled in the study. If the subject declines to participate, they will not be enrolled in the study.

The Investigator shall retain a copy of the signed informed consent document in each subject's record. All paper-based signed consents will be kept at the site and are only accessible to study team members. A copy of the signed consent and HIPAA/data protection authorization will be provided to the subject. The Investigator is also responsible for ensuring any new information which may affect the subject's health, welfare, or willingness to stay in the study will be provided to the subject. Subjects may need to be re-consented to continue participation if required by IRB.

7.6.2. Verification of Eligibility, and Participant Demographics

The Investigator and/or staff delegated for this task shall conduct screening assessments to verify eligibility criteria for the subject. If the subject does not meet all eligibility criteria, they will be notified and considered a screen failure.

Research staff will collect and record on the CRF the participant's demographic information, including but not limited to; age, self-identified; gender, race & ethnicity. Medical History will also be recorded on the CRF.

7.6.3. Allocation Concealment and Randomization

A block randomization algorithm will be utilized to generate the random allocation list. Participants will be randomly assigned to one of the two groups of active or sham in equal ratios.

7.6.4. Blinding and Unblinding Rules

A randomization table will be kept with the sponsor. Subjects and study site staff (investigators, researchers, care providers) will be blinded to the group assignment. Personnel involved in device placement will not be involved in subject care or study outcome data collection to avoid any potential bias. Should a subject experience an adverse event and the investigator deems unblinding necessary for appropriate care, the subject and research staff will be unblinded and the subject will be withdrawn from the study.

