7. DESIGN OF THE CLINICAL INVESTIGATION

7.1. General

This is a two-arm, prospective, randomized, double-blind, sham-controlled clinical trial. The sham control device will be identical in appearance to the active device but will not deliver electrical current. Enrolled participants will be randomly assigned an active or sham Bridge™ device based on the randomization scheme provided by the sponsor. Sponsor will sequentially number devices to ensure allocation concealment. Research staff placing the device will not collect data on the CRF for that subject to prevent any bias in data collection. Unblinding of participant's treatment assignment will only be broken if the health of the participant is at risk as determined by an onsite medical doctor.

Overview of tasks to be completed

1. Prescreening, consenting, eligibility verification, demographic, medical history data collection
2. Baseline assessments (*COWS, SOWS,* [REDACTED])
3. Randomization and Bridge placement
4. Assessments throughout the course of the study (See Table 1)
5. Study Follow-Up

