7.6.5. Assessments

Delegated research staff will administer the *COWS* [REDACTED] and provide the patient with the *SOWS* [REDACTED] [REDACTED] assessments to complete. Personnel involved in device placement will not administer the assessments to avoid any potential bias. Refer to Table 1 for time and frequency of assessments. Demographic information (i.e., age, gender, race, etc.) will also be collected and recorded on the CRF.

The instruments that will be used are listed below. Any changes to the listed assessments will be noted in the study records.

CLINICAL INVESTIGATION PLAN

Impact of Bridge™ device as a non-pharmacological approach to treat opioid withdrawal in opioid use disorder (OUD) subjects in an inpatient treatment center

DENE0001

Clinical Opiate Withdrawal Scale (COWS): COWS is an 11-item clinician administered scale used for measuring opiate withdrawal signs.⁶ The COWS takes approximately 2 minutes to complete. See Appendix I.

Subjective Opiate Withdrawal Scale (SOWS): SOWS is a self-reported rating scale measuring the experience of 16 symptoms on a Likert scale from 0 (not at all) to 4 (extremely).⁷ See Appendix II.

[REDACTED]

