14.4. Adverse Event Reporting

- All adverse events, both anticipated and unanticipated, must be recorded in the within the CRF and in the *Adverse Event Report Form*.
- All adverse events must be promptly reported to the sponsor.

Impact of Bridge™ device as a non-pharmacological approach to treat opioid withdrawal in opioid use disorder (OUD) subjects in an inpatient treatment center

DENE0001

- All unanticipated adverse device effects will be also reported to both the sponsor and the IRB.
- Both serious adverse events and unanticipated adverse device effects must be reported to the sponsor within 48 hours. All other adverse events should be reported to the sponsor within five business days.
- All serious adverse events will be also reported to the IRB per IRB reporting requirements. These reports may include but will not be limited to: date of onset, brief description of the events, their treatment, whether they resulted in death, participant hospitalization, severe or permanent disability or were life threatening, their relationship to the study device, and resolution.

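### Section 7.6.4 ties an adverse-event code break to unblinding the research staff and withdrawing the participant; neither step is needed for care, and rewording it is a cheap, low-severity improvement

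*Combined protocol and SAP*

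**What the plan says.** - **Trigger and consequences, Section 7.6.4.** The rule opens "Should a subject experience an adverse event and the investigator deems unblinding necessary for appropriate care" and continues "the subject and research staff will be unblinded and the subject will be withdrawn from the study". Both consequences are mandatory, and the staff group is not qualified.
- **Trigger, Section 7.1.** The blind "will only be broken if the health of the participant is at risk as determined by an onsite medical doctor". This names a different decision-maker and threshold, and mentions neither staff unblinding nor withdrawal.
- **Who rates, Section 7.6.5.** "Delegated research staff will administer the" COWS; SOWS is self-reported. The only separation of raters is from those who place the device: "Personnel involved in device placement will not administer the assessments to avoid any potential bias".
- **Allocation.** This is a single site (7.3) with sequentially numbered devices (7.1) and equal allocation. Section 7.6.3 says "A block randomization algorithm will be utilized to generate the random allocation list". Block size is not stated.
- **Withdrawal.** Section 7.5.4 lets a withdrawn participant be replaced. For removal of the device on request, 7.6.8 ends further assessments but allows earlier data to be used. Section 7.6.4 has no matching sentence on data.
- **Safety recording.** Section 9.3 requires CRFs for non-completers too, and 14.3 covers all events during device wear. Section 14.4 requires recording and prompt reporting; serious-event reports to the IRB may cover "their relationship to the study device, and resolution".
- **Missing data.** The power calculation in Section 8 assumes values are missing completely at random (MCAR).

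**The concern.** Treating a participant may require the treating clinician, and perhaps the participant, to learn the assignment. It does not require the staff who score the primary endpoint to learn it, or the participant to leave the study. By making both automatic, the rule has three costs.

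1. A randomized participant's remaining scores are lost for a reason tied to an adverse event. Such events may differ between a device that delivers current and one that does not, so MCAR is not plausible for these losses. Recruiting a replacement does not restore the participant who was randomized.
2. Raters who learn one assignment at a single site with balanced blocks may be able to guess others.
3. The plan does not say how the triggering event is followed once the participant has been withdrawn.

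Separately, staff facing an urgent event have two differently worded rules on who may break the code and when.

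**Working it through.** **1. The plan's own power figure.** Inputs from Section 8: 16 per arm, time-averaged difference 4.0, SD 5.04729, correlation 0.40, 9 measurements, two-sided 0.05.

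- Effective SD of a participant's mean under equal correlation: 5.04729 × √[(1 + 8 × 0.40)/9] = 5.04729 × √(4.2/9) = 3.448.
- Standard error: 3.448 × √(1/16 + 1/16) = 1.219.
- Power: Φ(4.0/1.219 − 1.96) = 0.9068, as stated.

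**2. Losses from one arm.** Replace one 1/16 by 1/(16 − k), where k evaluable participants are lost:

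| k lost | Power |
|---|---|
| 0 | 0.907 |
| 1 | 0.898 |
| 2 | 0.887 |
| 3 | 0.874 |
| 4 | 0.859 |

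This treats each lost participant as contributing nothing, which overstates the loss if scores before the break are used.

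**3. How often.** The documents give no code-break rate. For an assumed risk p per participant, the chance of at least one break among 48 is 1 − (1 − p)^48:

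| Assumed p | Chance of at least one | Expected number (48p) |
|---|---|---|
| 1% | 38% | 0.48 |
| 2% | 62% | 0.96 |
| 5% | 91% | 2.4 |
| 10% | 99% | 4.8 |

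**4. Inference about other participants.** Let b be the block size (assumed). With one assignment known, the best guess for another member of the same block is the opposite arm.

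- *Boundaries known:* P(correct) = (b/2)/(b − 1).
- *Only block size known, next-numbered participant:* that person is in the same block with probability (b − 1)/b; otherwise the guess is right half the time. So P(correct) = [(b − 1)/b] × [(b/2)/(b − 1)] + (1/b) × 0.5. For b = 4: 0.75 × 0.667 + 0.25 × 0.5 = 0.625.

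| b | Boundaries known | Only block size known |
|---|---|---|
| 2 | 100% | 75% |
| 4 | 67% | 62.5% |
| 6 | 60% | 58% |

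With no information the figure is 50%. The first column is an upper case.

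**5. Sections side by side.** Section 7.6.4 unblinds the research staff, and 7.6.5 draws the COWS raters from that group. No section limits disclosure to the treating clinician, reserves a blinded rater, or keeps the participant in outcome follow-up after a break. The two-week contact in 7.6.9 asks about the next level of care, not about the event.

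**The case against.** The strongest reply is that the rule largely contains its own damage. The participant is withdrawn in the same sentence, so staff do not go on scoring someone whose arm they know. This stands. A reader might infer that the rule leads to unblinded COWS ratings of that participant, and the documents do not support it.

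The second reply is that guessing other assignments needs knowledge the plan does not give to raters. Block size and boundaries are undisclosed, and the sponsor holds the randomization table. This also stands as a limit: the spill-over is possible, not demonstrated.

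The third concerns safety. A reader might infer that an unblinded participant loses all later safety follow-up, or drops out of an arm's safety set. Neither is supported. Sections 9.3, 14.3 and 14.4 still require recording and reporting, with no exemption for withdrawn participants. Section 14.4 says serious-event reports may include resolution, which does not contradict 7.6.4. Section 15.2 provides care for research injury. The text defines no safety set, and the triggering event would already be recorded. What survives is narrower: no follow-up after withdrawal is specified.

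Fourth, the investigator may also be the onsite doctor, and the two thresholds can coexist. That makes the difference between 7.1 and 7.6.4 a matter for harmonisation, not evidence of bias. Finally, the separate SAP that Section 8 mentions is not in the text available and may deal with data after a code break. It would not change who is unblinded or withdrawn under 7.6.4.

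**Conclusion.** The point holds as a cheap improvement of low severity. Section 7.6.4 spreads the assignment further than care requires and turns a code break into lost outcome data for an adverse-event-related reason. The missingness mechanism matters more than the power, which falls by about 0.01 for one participant lost from one arm and about 0.05 for four. Inference about other participants ranges from 58% to 100% correct over the assumed block sizes, against 50%, and only if raters know at least the block size.

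The conclusion rests on two readings: that the unqualified staff group in 7.6.4 includes the COWS raters, and that withdrawal from the study ends scheduled assessments, as 7.6.8 states for early device removal. The code-break rates and block sizes are assumptions. With no rate in the documents the effect cannot be fixed exactly, but it is expected to be small.

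**What to change.** Rewrite Section 7.6.4 so that:

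- the assignment is disclosed only to those who need it for care;
- COWS raters and other research staff stay blinded;
- a code break is not in itself a reason for study withdrawal;
- follow-up of the adverse event and scheduled COWS and SOWS continue if the participant consents, with SOWS flagged if the participant was told the assignment, because it is self-reported;
- the date, reason and recipient of each break go on the CRF.

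Reconcile Sections 7.1 and 7.6.4 so that they state the same decision-maker and threshold; which clinical rule applies is for the sponsor and investigator to settle. Whether the device stays on is likewise a clinical matter and outside this point.

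The cost is protocol wording, with no new participants or staff and no visits beyond those already scheduled. The small downside is that some scores may come from participants who know their assignment. A sensitivity analysis excluding scores after the break addresses that.

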7.6.5. Assessments

Delegated research staff will administer the *COWS* [REDACTED] and provide the patient with the *SOWS* [REDACTED] [REDACTED] assessments to complete. Personnel involved in device placement will not administer the assessments to avoid any potential bias. Refer to Table 1 for time and frequency of assessments. Demographic information (i.e., age, gender, race, etc.) will also be collected and recorded on the CRF.

The instruments that will be used are listed below. Any changes to the listed assessments will be noted in the study records.

CLINICAL INVESTIGATION PLAN

Impact of Bridge™ device as a non-pharmacological approach to treat opioid withdrawal in opioid use disorder (OUD) subjects in an inpatient treatment center

DENE0001

Clinical Opiate Withdrawal Scale (COWS): COWS is an 11-item clinician administered scale used for measuring opiate withdrawal signs.⁶ The COWS takes approximately 2 minutes to complete. See Appendix I.

Subjective Opiate Withdrawal Scale (SOWS): SOWS is a self-reported rating scale measuring the experience of 16 symptoms on a Likert scale from 0 (not at all) to 4 (extremely).⁷ See Appendix II.

[REDACTED]

7.6.6. Device Placement

The ear shall be cleaned with alcohol wipes and transilluminated to mark the vascular branches. The needles shall be placed in the dorsal and ventral aspects of the ear within 1–1.5 mm of the vascular branches, but not on main arterial branches. The generator will be attached with adhesive to the skin behind the ear just over the mastoid process. A photograph may be taken immediately after device placement to use as a reference for where the leads should be. No identifying features shall be captured on the photograph.

7.6.7. Symptom Control Medications

Symptom control medications such as phenobarbital, clonidine, cola syrup, melatonin, ibuprofen, promethazine, dicyclomine, loperamide should not be provided for 2 hours after Bridge placement. If the subject requires symptom control medications within 2 hours of device placement, medications should be provided and recorded on the CRF.

7.6.8. Device Removal

Medical staff trained and delegated will remove the Bridge device on Day 6. The device shall be disposed in a Sharps container, in accordance with Masimo's Bridge Device Training program, the Device Instructions for Use (DFU) and Operator's Manual.

If subject requests to remove the Bridge device prior to 5 days, they will be withdrawn from further study assessments and procedures, however their data collected up to the point of withdrawal may still be used for data analysis.

CLINICAL INVESTIGATION PLAN

Impact of Bridge™ device as a non-pharmacological approach to treat opioid withdrawal in opioid use disorder (OUD) subjects in an inpatient treatment center

DENE0001

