The intent of this study is to investigate the efficacy of Bridge™ in alleviating withdrawal symptoms in a prospective, sham-controlled setting. *COWS* and *SOWS* will be used to assess the severity of opioid withdrawal symptoms and as an outcome measure to assess treatment effect. *COWS* is a validated, clinically relevant, and reliable objective measure of therapeutic effect and clinical benefits, which is widely used in drug treatment protocols to assess the signs, symptoms, and severity of acute withdrawal, while *SOWS* is a subjective measure^(6, 7).

5. BENEFITS AND RISKS OF THE INVESTIGATIONAL DEVICE, CLINICAL PROCEDURE, AND CLINICAL INVESTIGATION

Anticipated benefits: There may be direct benefits to subjects participating in the active Bridge™ arm. There are no anticipated benefits to subjects who receive the sham device.

Device risks: Potential risks of percutaneous therapies, generally, include bleeding or infection at the puncture site, pain or skin irritation at the application site. Refer to the *Instructions for Use* for safety information, warnings, and cautions.

Contraindications: The device is contraindicated for use by patients with cardiac pacemakers, hemophilia, and psoriasis vulgaris. The device is also contraindicated for use in patients with a previous history of sensitivity to compound benzoin tincture, which is used to attach the electrodes to the ear.

Risk mitigation: Device shall be placed on intact skin only and subjects with cardiac pacemakers, hemophilia, and psoriasis vulgaris will be excluded from the study.

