7.4. Investigational Device(s) and Comparator(s)

Bridge™ is an FDA-cleared medical device for the treatment of symptoms related to opioid withdrawal. Participants will be assigned to one of two interventions: active device or sham device. The sham device will be identical in appearance to the active device but will have no electrical current.

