7.5.4. Participant Classifications

Participants will be classified according to the criteria below:

- **Screened** – Participants who are assessed for study eligibility after signing informed consent.
- **Enrolled** – Clinical trial participants who have met all inclusion criteria and do not meet any exclusion criteria and have been assigned a participant identification number.
- **Screen Failure** – Participants who do not meet all eligibility criteria. (Reason of the participant's ineligibility will be documented on a *Screening and Enrollment Log*).
- **Withdrawn** – Participants who do not complete study either because they voluntarily choose not to participate further in the study and withdraw their consent, or they are discontinued from the study per PI discretion. If a participant leaves the study prematurely or is withdrawn from the study, another participant may be recruited.
- **Lost to Follow-up** – Participant is unable to be reached for follow-up after 3 attempts. Research staff shall document on the CRF, and no further attempts will be made.
- **Completed** – Participants will be considered complete if they wear the Bridge™ for 5 days.

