8. STATISTICAL DESIGN AND ANALYSIS

This is a single site, two-arm, prospective, randomized, double-blind, sham-controlled clinical trial. The study's main outcomes are COWS and subjective opiate withdrawal scale (SOWS) scores, measured over 8 time periods: at baseline, 30, 60, 120 minutes, 2nd, 3rd, 4th, and 5th day.

The study design data results in correlated observations will be collected repeated measurements within clusters (i.e., patients). These correlations invalidate the independence assumption in commonly used univariate and multivariate statistical techniques such as t-tests and multiple linear regression. Therefore, the Generalized Estimating Equations (GEE) method was used to estimate the power and sample size, a flexible class of models that account for correlated observations and are a commonly used method for repeated data analysis. This class of model does not require the normality assumption and does not require the full specification of the joint distribution of repeated measurements. Further, the power/sample size for testing the time-averaged difference (TAD) between two means from continuous, correlated data that will be analyzed using the GEE method was calculated. Such data occur in two design types: clustered and longitudinal (repeated measurement). Time-averaged difference analysis is often used when the outcome to be measured varies with time.

The following parameter estimates are required for calculating the power:

1. Alpha (α): The probability of rejecting a true null hypothesis = 0.05
2. δ : The time-averaged difference at which the power is calculated. We estimated that the COWS time average is 2.8 for the Bridge group and 6.8 for the sham group, then $\delta = 4.0$.

The δ of 4.0 was selected such as to be conservative and taking into consideration:

Impact of Bridge™ device as a non-pharmacological approach to treat opioid withdrawal in opioid use disorder (OUD) subjects in an inpatient treatment center

DENE0001

- After the first two hours comfort medications and medication tapers may be administered to the control group thus the COWS score may be reduced
- After three days the withdrawal symptoms are anticipated to abate for both groups

The above rationale was discussed with and supported by Masimo Bridge device and OUD clinical experts.

The power was calculated for various TAD δ values 2.8, 3, 4 and 4.7 (see Figure 3).

3. σ : The standard deviation of a response (COWS): 5.047 (estimated, see Table 2 below).

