4. ρ : The base correlation between two responses on the same subject. We used the estimate calculated by the other statistician for the sample size calculation (0.40).
5. The treatment group allocation proportion is the proportion of subjects that are in the treatment group. The proportion is 1:1 (50%)
6. The number of time points at which each subject is measured: 9.
7. The time values represent the proportion of the total study time that has elapsed just before the measurement: 0, 0.003, 0.005, 0.01, 0.021, 0.25, 0.5, 0.75, 1, which are equivalent to: prior to device placement, 20 min, 30 min, 60 min, 120 min, 2nd day, 3rd day, 4th day and 5th day.

Data used for the sample size calculation was abstracted from the article by Adrian Miranda & Taca (2018)⁵.

Table 2. COWS Score Statistics Based on Article by Adrian Miranda & Arturo Taca (2018)⁵

Time (mins)	BRIDGE Group			
	Mean COWS	% Reduction	SD	n
0	20.1	0.0	6.1	73
20*	7.5	62.7	5.9	62
30	4.0	80.1	4.4	73
60	3.1	84.6	3.4	71
120	2.8	86.1	**	
1440 (Day 2)	2.1	89.6	**	
2880 (Day 3)	1.4	93.0	**	
4320 (Day 4)	1.0	95.0	**	
5760 (Day 5)	0.6	97.0		33
Average	2.8	86.0		
Pooled SD		5.047		

* 20 minutes measurement is not included in the study design; it was included from the article to enhance the estimates for the required parameters for the sample size/power calculations.

** The yellow highlighted values are estimated (extrapolated from the available data)

A sample of 32 subjects (16 in each group), each measured 9 times, achieve a power of 0.9068 when using a two-sided Wald test from a GEE analysis to test whether the time-average difference of the Bridge subjects differs from that of the sham subjects by more than 4.0 at a significance level of 0.05. The subjects are randomly split between a

[figure not shown]
Impact of Bridge™ device as a non-pharmacological approach to treat opioid withdrawal in opioid use disorder (OUD) subjects in an inpatient treatment center**DENE0001**

Bridge group and a sham group, with 50% of the subjects assigned to the Bridge group. The residual standard deviation is anticipated to be 5.04729. The measurements of each subject will be made at the following times expressed as proportions of the total study time: 0, 0.003, 0.005, 0.01, 0.021, 0.25, 0.5, 0.75, 1, which are equivalent to: prior to device placement, 20 min, 30 min, 60 min, 120 min, 2nd day, 3rd day, 4th day and 5th day. Missing values are assumed to occur completely at random (MCAR).

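### Section 7.6.8 ends COWS and SOWS scoring when a participant asks for early device removal, even if that person stays in the center and still consents, so possibly outcome-related scores go uncollected

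*Combined protocol and SAP*

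**What the plan says.** Section 7.6.8 (Device Removal) sets the consequence of a removal request: "If subject requests to remove the Bridge device prior to 5 days, they will be withdrawn from further study assessments and procedures". Earlier scores are not discarded: "their data collected up to the point of withdrawal may still be used for data analysis".

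Section 7.5.4 (Participant Classifications) describes withdrawn participants as people who do not complete because "they voluntarily choose not to participate further in the study and withdraw their consent, or they are discontinued from the study per PI discretion". Completion is tied to wear: "Participants will be considered complete if they wear the Bridge™ for 5 days". No category exists for a participant who is off the device but still followed.

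Section 8 says that COWS and SOWS are "measured over 8 time periods: at baseline, 30, 60, 120 minutes, 2nd, 3rd, 4th, and 5th day", which is seven scores after baseline. Missing completely at random appears there as an input to the power calculation. Section 8 also says that a separate statistical analysis plan exists. That plan was not supplied, and the schedule of events in Section 7.6.12 is redacted.

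**The concern.** The request alone stops the scoring; neither withdrawal of consent nor discharge is needed. Two plausible reasons for a request bear on the comparison. One is unrelieved withdrawal, which is what COWS measures. The other is local discomfort: Section 5 lists "pain or skin irritation at the application site" among the device risks. Section 7.4 says "The sham device will be identical in appearance to the active device but will have no electrical current", so both the frequency of requests and the reasons for them could differ by arm. That link is an inference, because the documents give no removal data.

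Scores recorded up to removal look the same whether the Bridge effect then persists, fades or ends. A given analysis of them returns one estimate, while the as-randomised effect differs between those cases. The missing scores would help to tell them apart, and they cannot be collected later. Bias is at stake here, not power.

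**Working it through.** **Plan's own figure.** Section 8 inputs: difference 4.0 (6.8 sham, 2.8 Bridge), SD 5.047, correlation 0.40, 16 per arm, 9 measurements, two-sided alpha 0.05.
- SD of a participant's average: 5.047 × √((1 + 8 × 0.40)/9) = 3.448.
- SE: 3.448 × √(2/16) = 1.219.
- Power: Φ(4.0/1.219 − 1.96) = 0.9068, as stated.

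**Yardstick.** With 24 complete per arm and the seven post-baseline scores, SE = √(2 × 5.047² × (1 + 6 × 0.40)/7/24) = 1.015.

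**Case 1: symptom-driven removal, same rule in both arms.** Scores are exchangeable normal with the inputs above. Assumptions: removal before Days 2 to 5, with log-odds rising by 0.2 to 0.3 per COWS point of the last recorded or the current unseen score. Two analyses of the scores available under 7.6.8 are compared with the as-randomised truth, 4.0 × (1 − q × f). Here q is the share of Bridge post-baseline scores falling after removal, and f is the fraction of effect lost (0, 0.5 or 1).

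| Removal overall | Visit-adjusted, available data | Likelihood-type, arm by visit | Truth: effect persists | Half lost | Ends |
|---|---|---|---|---|---|
| 10% (q 1.9–2.3%) | 3.86–3.95 | 3.92–4.00 | 4.00 | 3.95–3.96 | 3.91–3.92 |
| 33% (q 8.1–9.0%) | 3.67–3.88 | 3.78–4.00 | 4.00 | 3.82–3.84 | 3.64–3.68 |
| 50% (q 14.3–15.3%) | 3.59–3.85 | 3.69–4.00 | 4.00 | 3.69–3.71 | 3.39–3.43 |

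Largest gaps:
- At 10%: (4.00 − 3.86)/1.015 = 0.14 SE, an understatement.
- At 50%: (4.00 − 3.39)/1.015 = 0.60 SE, an overstatement.

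The likelihood-type model is unbiased when removal depends only on recorded scores and the effect persists, and not in general otherwise.

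**Removal also possible before the 30, 60 and 120 minute scores.**
- At 10%, the visit-adjusted estimate is 3.79–3.92. The largest gap is (4.00 − 3.79)/1.015 = 0.21 SE.
- At 50%, the visit-adjusted estimate is 3.20–3.72, the likelihood-type estimate 3.35–4.00, and the truth if the effect ends 3.02–3.20.
- The understatement at 50% reaches (4.00 − 3.20)/1.015 = 0.79 SE.
- The overstatement at 50% is at most (4.00 − 3.02)/1.015 = 0.97 SE. This is an outer limit, because those two ends come from different settings. Within one setting, a rerun gives q = 21.4%, so the truth is 4.0 × (1 − 0.214) = 3.14 and the gap from 4.00 is 0.86/1.015, about 0.8 SE.

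**Case 2: discomfort, Bridge arm only, unrelated to COWS (assumption).** If 20% of Bridge participants remove (10% overall, about 5 people), q is 7.3%. Both analyses return 4.00. The truth is 4.0 × (1 − 0.073/2) = 3.85 if half the effect is lost and 4.0 × (1 − 0.073) = 3.71 if it ends. The latter gap is 0.29/1.015 = 0.29 SE.

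**Direction.** A separate simulation had 24 per arm, scoring lost after 120 minutes and a persisting effect.
- Random removal: bias within 0.03.
- The worst scorers removed equally in both arms: about 0.
- The worst scorers removed at 17% of Bridge and 50% of sham: −0.36.
- The same with the rates reversed: +0.35.
- Opposite reasons in the two arms, 50% each: about ±0.9.

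**Dependence on the outcome curve.** The flat 6.8 against 2.8 is a simplification. With the Table 2 means and an assumed difference of 2 on Days 2 to 5 (average still 4.0), the worst likelihood-type bias at 50% falls from 0.31 to 0.18 if the effect persists. If it ends, the bias falls from 0.61 to about 0.35. The visit-adjusted estimate does worse (4.42 against a truth of 3.67), because it gives more weight to early visits, where the difference is larger.

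**Limit.** The normal model puts Φ(−2.8/5.047) = 29% of Bridge scores below zero, so the figures show order of size only.

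**The case against.** The strongest reply is that the rule suits an on-device question. Section 6 frames its hypotheses around participants on the active device, and completion means five days of wear. On that reading, much of the gap in the cases where the effect fades or ends reflects a choice of target. This stands in part: recorded scores can still address an on-device question. But the trial is randomised, and collecting the later scores keeps that analysis while also allowing the as-randomised one.

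Four stronger readings are tempting, and the documents do not support them.
- A reader might infer that the bias cannot be assessed at all. Pre-removal scores may be used, and delta-adjusted or tipping-point analyses can bound it. What is lost is any observed post-removal score to test the assumptions against.
- A reader might infer that 7.6.8 contradicts 7.5.4. The wording there does not clearly cover a request to stop the device while consent stands. However, discontinuation at the investigator's discretion might cover it, and 7.6.8 itself calls the event withdrawal. The sections need aligning; a contradiction is not shown.
- A reader might infer that half the participants are expected to remove the device. The 50% in Section 8 pools dropout with missing COWS, and going from 48 to 32 is a loss of 1 − 32/48 = 33%. Early removers do not count as completers, so they fall within that allowance, but their share is not stated.
- A reader might infer that missing-data handling is absent. It may be in the separate plan. That plan cannot supply scores never taken, though the redacted schedule means that a score at the moment of removal cannot be excluded.

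**Conclusion.** The point holds as an avoidable loss of primary-endpoint data, and correcting it is a cheap improvement. At an assumed 10% removal the bias is small: about 0.1 to 0.2 SE if symptom-driven. It is about 0.3 SE against the as-randomised effect if removal is Bridge-only discomfort and the effect ends. At an extreme 50% it is roughly 0.6 SE, or 0.8 to 1 SE if removal can also occur in the first two hours. It can go either way and depends on the analysis model. It is near zero if removal is random or alike in both arms and the effect persists. Removal rates, slopes and persistence are all assumptions. A reader might infer that the trial's result would be biased toward Bridge; nothing in the documents establishes a direction, or that any bias will be material. Confidence is medium.

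**What to change.** Amend 7.6.8 along these lines: *A request for early removal ends device wear only. Unless the participant withdraws consent, scheduled COWS and SOWS continue through Day 5 while the participant remains in the center. The time of and reason for removal are recorded. All observed scores are used in the as-randomised analysis; on-device scores are kept for a supplementary analysis.* The removal decision itself is untouched.

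Also:
- Align 7.5.4 with this text.
- Flag post-removal scores and, where existing staffing allows, do not tell the rater the reason for removal.
- Handle participants unblinded under 7.6.4 separately.
- Confirm that the separate analysis plan uses these scores and has a missing-data sensitivity analysis.

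**Gain.** If every remover stays and is rated without bias, the as-randomised effect is recovered by construction. If half stay (assumption; case 1 at 50%), simple pooling cuts the worst bias from 0.41 to 0.11 (effect persists), 0.31 to 0.13 (half lost) and 0.61 to 0.26 (ends), though some settings gain nothing. Letting scored removers represent unscored ones of the same arm and visit recovers the truth within 0.01, provided staying is unrelated to score.

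**Cost.** A protocol amendment with IRB approval, possible re-consent, CRF changes and a check of the analysis plan. Each early remover needs at most 7 further COWS ratings, or 4 or fewer after the 120-minute score. At the 2 minutes each given in Section 7.6.5, 4 to 7 ratings come to 0.7–1.2 hours for 5 removers (5 × 4 × 2 = 40 minutes to 5 × 7 × 2 = 70 minutes) and 3.2–5.6 hours for 24. SOWS self-completion is extra. No new patients or staff are needed.

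**Downsides.** Raters may see that the device is off, people who leave the center are not recovered, and the as-randomised effect may be smaller than the on-device effect.
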